### **g) Specimen Banking**

There will be no specimens collected in this study.

### **h) Data Management and Confidentiality**

|   |  |
|---|--|
| Protocol Title:                           | QUADRATUS LUMBORUM II BLOCK VS CONVENTIONAL THERAPY ALONE FOR LAPAROSCOPIC SLEEVE GASTRECTOMY  |
| Principal Investigator Name/Contact Info: | [name] MD
[contact]   |
| Primary Contact Name/Contact Info         | [name] MD
[contact]
[contact]
[name] MD
[contact]
[contact]
[name] MD
[name] MD
[name] DO
[name] MD |
| Date Revised:                             | 1/10/2018  |
| Study Number:                             | IF 2203362   |

Data will be stored in a locked cabinet in the Anesthesia offices at Mount Sinai St. Luke's Hospital.

The patients' MRN numbers will be matched to the study number in an encrypted database on shared drives which will be located solely on the Mount Sinai Network computers to ensure protection of Protected Health Information. Study data will be stored in a separate encrypted database with subject data linked to study number.

The information included in the data will be medical record number, age, gender, time to first narcotic, total narcotic use, pain scores during the first 48 hours after surgery. Extent of blockade as determined by pin prick, itching, nausea, vomiting, and respiratory rate, heart rate, and blood pressure will be recorded on arrival, 1 hour after arrival to PACU and then on departure from PACU. PACU length of stay, location of pain.

Only the research personnel will have access to the data. The data will be stored as a hard copy files and on a secure database. The research personnel are responsible for the receipt of the data. The PI will keep the hard copies secure and any electronic data will be encrypted. No personal identifiers will be used. The data will undergo statistical analysis.

|   |  |
|---|--|
| Protocol Title:                           | QUADRATUS LUMBORUM II BLOCK VS CONVENTIONAL THERAPY ALONE FOR LAPAROSCOPIC SLEEVE GASTRECTOMY  |
| Principal Investigator Name/Contact Info: | [name] MD
[contact]   |
| Primary Contact Name/Contact Info         | [name] MD
[contact]
[contact]
[name] MD
[contact]
[contact]
[name] MD
[name] MD
[name] DO
[name] MD |
| Date Revised:                             | 1/10/2018  |
| Study Number:                             | IF 2203362   |

### i) Provisions to Monitor the Data to Ensure the Safety of subjects

Subjects will be monitored to detect complications our study protocol. If complications from the QL 2 block are detected or it is ascertained that that the infiltration group is doing significantly better than the QL 2 group, we will reassess whether or not it is ethical to randomize the patient pool.

Subjects will be informed that they can ask questions or review or discuss information pertaining to the study at any time before or during the consent process, as well as, during or after the intervention.

Subjects will be approached in the preadmission testing clinic at Mount Sinai-St. Luke's Hospital prior to the day of surgery. The patient's treatment team will continue to provide their standard care without interruption, regardless of whether or not the patient participates in the study, and regardless of group assignment.

Patients who wish to discuss the study in a private area will have that option available to them.

Part I: Elements of Data and Safety Monitoring Plan

|   | Primary Contact Name/Contact Info         | [name] MD
[contact]
[contact]
[name] MD
[contact]
[contact]
[name] MD
[name] MD
[name] DO
[name] MD |
|   | Date Revised:                             | 1/10/2018  |
|   | Study Number:                             | IF 2203362   |
|   |   |  |

*Academic Title:* Attending Physician, Assistant Professor

*Department:* Anesthesiology

*Mailing Address:* Mount Sinai St Luke's [name]

*[contact]

*Fax:*

*E-mail:* [[contact]](mailto:[contact])

Adverse events will be monitored as a standard of care everyone receives regardless of participation in the study. The safety and data information will be reviewed on a daily basis until the desired sample size is achieved. All temporary and/or permanent suspensions will be reported.

### j) Withdrawal of Subjects

Patients are free at any time to withdraw from the study. If they do so, their information will not be included in the study.

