### 4)Resources Available to Conduct the Human Research

For n=110, the feasibility of recruitment is manageable as we perform 5-10 sleeve gastrectomies per week on average. Recruitment will be done through a coordination of the operating schedule and the surgeon's office. Patients presenting for preoperative visits at the preoperative testing clinic will be approached. Patients routinely are seen by anesthesiologists at the preoperative testing clinic as part of their anesthetic evaluation. Patients will be approached by research personnel only if the patients are agreeable to the study and details of the study will be explained. The consent will be obtained in the pre operative testing clinic or in the pre operative holding area after all questions are thoroughly answered. The staff members on this protocol are all employees of Mount Sinai and will either be a resident or attending

|   |  |
|---|--|
| Protocol Title:                           | QUADRATUS LUMBORUM II BLOCK VS CONVENTIONAL THERAPY ALONE FOR LAPAROSCOPIC SLEEVE GASTRECTOMY  |
| Principal Investigator Name/Contact Info: | [name] MD
[contact]   |
| Primary Contact Name/Contact Info         | [name] MD
[contact]
[contact]
[name] MD
[contact]
[contact]
[name] MD
[name] MD
[name] DO
[name] MD |
| Date Revised:                             | 1/10/2018  |
| Study Number:                             | IF 2203362   |

physicians that are included on the IRB protocol. There are seven primary members of the research personnel:

a) [name]. – Roles for [name] in this study include serving as primary investigator responsible for study design and planning, data collection, subject recruitment, manuscript writing and preparation, data analysis, safety monitoring, and responding to adverse events and/or complications. He is certified in PPHS/IRB protocols, all Citi/IRB required training in human subject protection, and has prior clinical research experience. He is also a board certified anesthesiologist and assistant professor of anesthesiology with the Icahn School of Medicine and the Mount Sinai Health System.

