The QL 2 group will receive 15 mL bupivacaine 0.25% on both sides for a total of 30 mL once the surgery is done but prior to extubation.

Then anesthesiologist performing the QL 2 block will be different from the anesthesiologist assessing the patient after surgery.

The patient and anesthesiologist assessing the patient will be blinded.

|   |  |
|---|--|
| Protocol Title:                           | QUADRATUS LUMBORUM II BLOCK VS CONVENTIONAL THERAPY ALONE FOR LAPAROSCOPIC SLEEVE GASTRECTOMY  |
| Principal Investigator Name/Contact Info: | [name] MD
[contact]   |
| Primary Contact Name/Contact Info         | [name] MD
[contact]
[contact]
[name] MD
[contact]
[contact]
[name] MD
[name] MD
[name] DO
[name] MD |
| Date Revised:                             | 1/10/2018  |
| Study Number:                             | IF 2203362   |

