### **c) Number of Subjects**

**110**

The sample size was determined by *a priori* power analysis, two-tailed, with effect size of 0.7 (mild-moderate effect), alpha error 0.05, power 0.95.

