### **d) Study Timelines**

One year

|   |  |
|---|--|
| Protocol Title:                           | QUADRATUS LUMBORUM II BLOCK VS CONVENTIONAL THERAPY ALONE FOR LAPAROSCOPIC SLEEVE GASTRECTOMY  |
| Principal Investigator Name/Contact Info: | [name] MD
[contact]   |
| Primary Contact Name/Contact Info         | [name] MD
[contact]
[contact]
[name] MD
[contact]
[contact]
[name] MD
[name] MD
[name] DO
[name] MD |
| Date Revised:                             | 1/10/2018  |
| Study Number:                             | IF 2203362   |

2018-2019 and subsequent data analysis. The subject's participation will be from time of enrollment in the pre-operative period until first 48 hours after surgery. Estimated date of enrollment completion will be when 110 eligible subjects are enrolled in final data analysis. Estimate date for study completion will be 2019.

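### The withdrawal rule removes data already recorded for randomised and treated patients; the expected bias is small, but the wording should be limited

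*Protocol*

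**What the plan says.** Protocol section 5 j), Withdrawal of Subjects, has two sentences. The first sets no limit on timing: "Patients are free at any time to withdraw from the study". The second gives the consequence: "If they do so, their information will not be included in the study". It has no exception for patients already randomised or treated, or for data already recorded.

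Section 5 d), Study Timelines, defines the period in which a patient can withdraw: "participation will be from time of enrollment in the pre-operative period until first 48 hours after surgery". Section 5 b), Recruitment Methods, places the wound infiltration and the QL 2 block at the end of surgery. The primary outcome in section 5 e), Study Endpoints, is opioid use over the 48 hours that follow. Section 5 h) lists the matching data item: "total narcotic use, pain scores during the first 48 hours after surgery".

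**The concern.** Randomisation supports a comparison of the groups as they were allocated. A rule that deletes a patient's data because of something that happens after allocation can break that comparison. Here the whole primary outcome window follows treatment, so a patient who leaves at, say, 24 hours has been randomised and treated and has part of the opioid total on record. Under section 5 j) all of it goes.

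If the patients who leave differ in opioid use from those who stay, and leave more often in one arm, the difference between arms is shifted. Loss of heavy users from the control arm would hide a benefit of the block; loss from the QL arm would overstate one. Read literally, the rule also removes any complication recorded for a treated patient who then leaves, although section 5 i) relies on detected complications when judging whether randomisation is still ethical. Clinical monitoring of adverse events continues for everyone, so what is lost is study data, not care.

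**Working it through.** **Step 1: whom the rule reaches.** Withdrawal is possible at any time (5 j). Participation ends 48 hours after surgery (5 d). Treatment is at the end of surgery (5 b). The exact time of randomisation is not stated, but on any reading it comes before treatment. The rule therefore covers randomised and treated patients for the full 48 hours.

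**Step 2: the plan's own figure.** Section 5 c) gives 110 subjects, "two-tailed, with effect size of 0.7 (mild-moderate effect), alpha error 0.05, power 0.95". A two-sample t-test with 1:1 allocation (assumed; the ratio is not stated) needs 54.02 per arm, so 55 per arm or 110 in total. Power at 55 per arm is 95.3%. The figure reproduces, with no allowance for loss, so 110 is the number needed in the analysis.

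**Step 3: size of a possible bias.** The protocol gives no withdrawal rate, so these inputs are assumptions:
- normal outcome with SD 1, two-sided t-test at 0.05, 55 analysed per arm;
- a fraction p of one arm leaves and nobody leaves the other;
- leavers are a random draw from the upper half of opioid users, whose mean is √(2/π) = 0.798 SD above the overall mean.

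Shift in the mean of the depleted arm = −p × 0.798 / (1 − p). For p = 0.05: −0.05 × 0.798 / 0.95 = −0.042 SD. For p = 0.10: −0.10 × 0.798 / 0.90 = −0.089 SD.

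Type I error is the rejection probability of the t-test (108 degrees of freedom) with noncentrality = shift × √(55/2). For p = 0.10: 0.089 × 5.244 = 0.46, which gives 7.5%. The simulated columns come from 100,000 trials per row; power is at a true difference of 0.7 SD with the loss in the control arm.

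| One-arm loss | Shift (SD) | Type I error, analytic | Type I error, simulated | Power, simulated |
|---|---|---|---|---|
| none | 0 | 5.0% | 4.9% | 95.3% |
| 2% | 0.016 | 5.1% | 5.1% | 94.6% |
| 5% | 0.042 | 5.5% | 5.6% | 92.9% |
| 10% | 0.089 | 7.5% | 7.6% | 89.1% |
| 15% | 0.141 | 11.3% | 11.6% | 83.4% |

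When both arms lose patients, only the imbalance matters. With 10% against 5%, the net shift is 0.089 − 0.042 = 0.047 SD and type I error is 5.7%. With 10% in each arm, simulated type I error is 5.0%. A right-skewed outcome (gamma, shape 2) gives similar values, for example 7.2% at 10% one-sided loss.

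**Step 4: what these rates mean in patients.** For 55 to remain after 10% leave, 55 / 0.90 = 61.1 must be randomised to that arm, so about 6 leave, all from the upper half of opioid users and none from the other arm. At 2%, 55 / 0.98 = 56.1, so about one patient leaves.

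**The case against.** The best defence is that few people will be affected and that the design works against bias. Section 5 b) says "The patient and anesthesiologist assessing the patient will be blinded", so a patient has no knowledge of the arm to act on. Treatment is given once, so there is no later discontinuation to prompt withdrawal. Section 5 f) specifies as-needed opioid for all patients, and section 5 i) says standard care continues regardless of participation, so a patient in pain gains no treatment by leaving. The rule also covers only patients who choose to leave the study; a block abandoned for poor visualisation, or a missed assessment, does not trigger it. All of this stands, and it is why the point is minor.

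It can also be said that the rule respects a patient's wishes about their data, and that the consent form may promise the same. That is a real purpose. It is why later chart collection should depend on permission and why the consent wording must agree. It does not require deleting everything recorded before withdrawal by default.

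A third defence is that analysis sets and missing data belong in the SAP. That is true of the method details, and their absence is no finding. But the protocol itself fixes this exclusion, and an SAP that kept these patients would have to contradict it.

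Two stronger readings are tempting and not supported. A reader might infer that the result will be biased. The documents do not show that anyone will withdraw, that rates will differ by arm, or that leaving will depend on opioid use. A reader might also infer from section 5 d), "Estimated date of enrollment completion will be when 110 eligible subjects are enrolled in final data analysis", that withdrawals will be replaced out of sight, or that 110 is used inconsistently because section 4 says "For n=110, the feasibility of recruitment is manageable". But 110 analysed is what the power calculation gives (step 2), section 4 speaks only of feasibility, and nothing says that withdrawals will go unreported.

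**Conclusion.** The concern holds as a minor point of wording. Section 5 j) does not separate withdrawal before randomisation, which does no harm, from withdrawal after it, and so it discards recorded outcome and safety data of treated patients.

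Under the assumptions in step 3, type I error stays at about 5.1% to 5.5% for one-sided loss of 2% to 5%. It becomes material, at about 7.5%, only when some 10% of one arm leaves for reasons tied to opioid use. Nothing in the protocol points to that, and the size and direction of any actual bias are unknown. The case for changing the text is that the change is cheap and restores the as-randomised comparison.

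**What to change.** Replace the second sentence of Protocol section 5 j) with:

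> A subject who withdraws before randomisation is not analysed. For a subject who withdraws after randomisation, study procedures stop, data recorded up to withdrawal are kept and, where the subject permits, charted opioid doses to 48 h are still collected; the subject is analysed in the arm assigned.

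Align the consent wording, so that patients are told what happens to their data if they leave.

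The cost is one short amendment and some incomplete 48-hour totals, to be handled as the SAP specifies. Opioid use over 48 hours is already a listed data item, so no new measurement is needed; whether a withdrawn patient's chart may be read depends on the consent given.

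Leave section 5 d) and the number 110 unchanged. Recounting 110 as randomised subjects would lower power below the stated 0.95: to 94.2% with 104 analysed and 93.2% with 99.

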### 6) Risks to Subjects

Systemic absorption or intravascular injection of 0.25% bupivacaine or any other preparation of amide local anesthetics

|   |  |
|---|--|
| Protocol Title:                           | QUADRATUS LUMBORUM II BLOCK VS CONVENTIONAL THERAPY ALONE FOR LAPAROSCOPIC SLEEVE GASTRECTOMY  |
| Principal Investigator Name/Contact Info: | [name] MD
[contact]   |
| Primary Contact Name/Contact Info         | [name] MD
[contact]
[contact]
[name] MD
[contact]
[contact]
[name] MD
[name] MD
[name] DO
[name] MD |
| Date Revised:                             | 1/10/2018  |
| Study Number:                             | IF 2203362   |

can result in both central nervous system (CNS) and cardiac toxicity. Signs of CNS toxicity include restlessness, anxiety, dizziness, tinnitus, blurred vision, or tremors leading to convulsions. Such signs of CNS toxicity cannot be detected when the patient is under general anesthesia. Signs of cardiac toxicity include atrioventricular block, ventricular arrhythmias, and cardiac arrest. Patients will be monitored continuously during and after the procedure and will be given immediate treatment for local anesthetic toxicity if they exhibit the signs. Furthermore, the injection is performed in a relatively avascular anatomical space and both intravascular injection and systemic absorption are relatively unlikely.

Misplacement of the needle into the peritoneum and/or bowel is possible. Ultrasound guidance will be used and if the proper visualization of the needle is not possible, the procedure will be discontinued.

Bruising at the site of injection is possible.

## 7)Provisions for Research Related Injury

If subjects have an adverse reaction as a result of participation in the study, they will be given treatment and follow up for the adverse event at Mount Sinai St. Luke's Hospital free of charge.

## 8)Potential Benefits to Subjects

|   |  |
|---|--|
| Protocol Title:                           | QUADRATUS LUMBORUM II BLOCK VS CONVENTIONAL THERAPY ALONE FOR LAPAROSCOPIC SLEEVE GASTRECTOMY  |
| Principal Investigator Name/Contact Info: | [name] MD
[contact]   |
| Primary Contact Name/Contact Info         | [name] MD
[contact]
[contact]
[name] MD
[contact]
[contact]
[name] MD
[name] MD
[name] DO
[name] MD |
| Date Revised:                             | 1/10/2018  |
| Study Number:                             | IF 2203362   |

Benefits of QL 2 block in the context of bariatric surgery are unknown. Possible benefits that have been described in the literature include improved quality and duration of analgesia, reduced opioid consumption, reduced incidence of nausea and vomiting, and reduced incidence of constipation. There may not be any benefits.

## 9)Provisions to Protect the Privacy Interests of Subjects

Patients will be reassured that any identifying information will not be released. The patient's name, medical record number or any other information that identifies a patient will not be included in any data analysis. Patients will be contacted by phone from the research office at Mount Sinai St. Luke's Hospital.

## 10Economic Impact on Subjects

Patients will not incur any additional costs as the QL 2 block is a widely used method of analgesia for laparoscopic surgery.

## 11)Payment to Subjects

Patients will not receive compensation for this project.

|   |  |
|---|--|
| Protocol Title:                           | QUADRATUS LUMBORUM II BLOCK VS CONVENTIONAL THERAPY ALONE FOR LAPAROSCOPIC SLEEVE GASTRECTOMY  |
| Principal Investigator Name/Contact Info: | [name] MD
[contact]   |
| Primary Contact Name/Contact Info         | [name] MD
[contact]
[contact]
[name] MD
[contact]
[contact]
[name] MD
[name] MD
[name] DO
[name] MD |
| Date Revised:                             | 1/10/2018  |
| Study Number:                             | IF 2203362   |

## 12)Consent Process

Whenever possible, patients will be introduced to the study during their visit to the preoperative assessment clinic several days before the date of their operation by the PI, sub-investigators, or other members of the research team. When this is not possible, recruitment for the study will occur when patients are assessed in the holding area on the day of surgery. Neither children nor cognitively impaired patients, as determined by ability to consent to the procedure, will be recruited.

## 13)Process to Document Consent in Writing

The standardized IRB consent template will be used.

## 14)Vulnerable Populations

Not applicable.

## 15)Multi-Site Human Research (Coordinating Center)

Not applicable.

|   |  |
|---|--|
| Protocol Title:                           | QUADRATUS LUMBORUM II BLOCK VS CONVENTIONAL THERAPY ALONE FOR LAPAROSCOPIC SLEEVE GASTRECTOMY  |
| Principal Investigator Name/Contact Info: | [name] MD
[contact]   |
| Primary Contact Name/Contact Info         | [name] MD
[contact]
[contact]
[name] MD
[contact]
[contact]
[name] MD
[name] MD
[name] DO
[name] MD |
| Date Revised:                             | 1/10/2018  |
| Study Number:                             | IF 2203362   |

## 16)Community-Based Participatory Research

Not applicable.

## 17)Sharing of Results with Subjects

Results will not be shared with the subjects.

## 18)External IRB Review History

Not applicable.

## 19)Control of Drugs, Biologics, or Devices

*Note: The IDS has its own forms that must be completed and a review process that must be followed before the IDS representative will sign off on Appendix B for submission to the PPHS.*

Not applicable.
